7.0 OUTCOME MEASURES

7.1 Outcome Measures

Primary outcome measures will include:

1. OUD diagnosis (in the problem list or as an ICD-10 visit code) within 30 days of index visit for patients identified by the OUD-CDS as being at high risk of OUD
2. Naloxone prescription within 30 days of index visit for patients with OUD or identified by the OUD-CDS as being at high risk for OUD
3. MOUD orders or referral to OUD treatment within 30 days of index visit for patients with OUD or identified by the OUD-CDS as being at high risk for OUD
4. Total days covered by an MOUD prescription in the 90 days after index visit for patients with OUD or identified by the OUD-CDS as being at high risk for OUD

Secondary outcome measures will include:

1. OUD diagnosis (in the problem list or as an ICD-10 visit code) at index or within 90 days of index visit for patients identified by the OUD-CDS as being at high risk of OUD
2. Naloxone prescription at index or within 90 days of index visit for patients with OUD or identified by the OUD-CDS as being at high risk for OUD
3. MOUD orders or referral to OUD treatment at index or within 90 days of index visit for patients with OUD or identified by the OUD-CDS as being at high risk for OUD
4. Number of ED visits during the observation period for patients with OUD or identified by the OUD-CDS as being at high risk for OUD
5. Number of hospitalizations during the observation period for patients with OUD or identified by the OUD-CDS as being at high risk for OUD
6. Healthcare costs during the observation period for patients with OUD or identified by the OUD-CDS as being at high risk for OUD, compared with healthcare costs over the same interval preceding the observation period
7. Cost of OUD-CDS implementation and maintenance
8. All-cause mortality rates during the observation period for patients at high risk of OUD
9. Fatal and non-fatal opioid overdoses during the observation period for patients at high risk of OUD
10. Rates of OUD-CDS use in intervention clinics
11. PCP ratings of confidence in treating patients with OUD prior to go-live date and 9 months following go-live date
12. Intervention clinic PCP ratings of satisfaction and acceptability of the OUD-CDS at 9 months following go-live date

Exploratory outcome measures may include:

1. Number of non-waivered PCPs becoming buprenorphine waived during the intervention period, assessed via health system administrative data
2. Number of buprenorphine prescriptions written by waived PCPs during the intervention period

3. PCP ratings of likelihood to prescribe buprenorphine for patients with OUD should no waiver be required, measured prior to go-live dates and at 9-months following go-live dates
4. Adherence to therapy during the observation period, assessed via Clarity and claims data
5. Number of patients diagnosed with OUD screened for mental health comorbidities and infectious diseases during the observation period

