11.0 STUDY ASSESSMENTS

11.1 Table of Assessments

Table 1. Assessment of Primary, Secondary and Exploratory Outcomes

Outcome	Timing*	Data Source
OUD diagnosis	Index date, 30 days, 90 days	EHR/OUD-CDS data
Naloxone prescription	Index date, 30 days, 90 days	EHR/OUD-CDS & Claims data
MOUD orders or referral	Index date, 30 days, 90 days	EHR/OUD-CDS & Claims data
days covered by MOUD prescription	Index date, 30 days, 90 days	EHR data
ED visits	Observation period	EHR & Claims data
Hospitalizations	Observation period	EHR & Claims data
Health care costs	Observation period, with pre-observation period matched for number of days	EHR & Claims data
Costs of OUD-CDS implementation and maintenance	Mid-intervention period	Interviews/surveys with implementation site staff
All-cause mortality	Observation period	EHR data, Claims data, State mortality data
Opioid overdoses	Observation period	EHR & Claims data
OUD-CDS use rates	Intervention period	EHR/OUD-CDS data
PCP confidence in treating patients with OUD	Baseline, 9 months	PCP surveys
PCP ratings of likelihood to prescribe buprenorphine for patients with OUD should no waiver be required	Baseline, 9 months	PCP surveys
Intervention PCP ratings of OUD-CDS satisfaction and acceptability	9 months	PCP surveys
Waivered PCPs	Pre-intervention, intervention period	Administrative data
Buprenorphine prescriptions written by waivered PCPs	Intervention period	EHR/OUD-CDS data
Adherence to therapy	Intervention period	EHR/OUD-CDS data
Screening for comorbid conditions	Observation period	EHR/OUD-CDS data

*Definitions:
 
Index Date
 
 ▪ Varies by patient ▪ First visit at which the OUD-CDS identifies that the patient is study eligible 
Intervention Period
 
 ▪ Varies by system ▪ OUD-CDS implementation date through a predetermined time at which the Wizard interfaces will be turned off in the intervention clinics 
Observation Period
 
 ▪ Varies by patient ▪ Index visit date through a predetermined time at which no more outcome data will be included in the analytic sample

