13.7 Missing Data and Dropouts

We expect person-based missingness to be extremely rare. Patients are unlikely to be aware that their data are being used for this research. They will not be consented and are unlikely to request that their data be excluded from analyses. Only patients who have requested that their data not be used for research and appear on site-maintained opt out lists will be excluded.

The primary data source for the Aim 1 through 3 hypotheses will be gathered from EHR-based data repositories at each participating site. The stored EHR data elements required for calculating the primary and secondary outcomes are extracted from live production tables. Medical care costs for Aim 4 will come from administrative claims systems that are relied upon for reimbursement of medical care services. The absence of documentation of a care process, vital sign, or medication should not be interpreted as a missing value but rather as indicative of a care process or test not having been performed or medication not prescribed within the health system. Likewise, absence of utilization indicated by billing claims almost always indicates that the utilization (such as a hospitalization) did not occur. Truly missing field-based observations (e.g., OUD diagnosis assigned, action not observed) will be extremely rare, undetectable and assumed to be missing at random.

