13.9 Safety Analysis

We will assess the rates of ED use, hospitalization and opioid overdoses that occur in intervention and control clinics during each patient's observation period. The rate at which each of these outcomes occurs per patient-year will be compared across clinics using generalized estimating equations. Clinic-aggregated counts of ED visits and inpatient stays will be normalized using a Poisson-Normal link function, and the intercept offset by the log of patient-years within the clinic. The model will estimate fixed effects of OUD-CDS, care system and other covariates on the rate of each outcome per patient-year. Should it be feasible, we will also collect and estimate the rate at which these events occurred in the year prior to each patient's index visit so that treatment group differences in pre-post changes in event rates can be quantified (i.e., treatment by time interaction).

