14.16.2 Safety Events

This study is being conducted at the provider level using CDS prompts for evidence-based best practice standards related to OUD. As such, we are not trying to change the standard of care for OUD in primary care, but rather to help PCPs achieve this standard of care in their care of patients with OUD. Prior to implementation, we will train all intervention PCPs and their rooming staff on the importance of helping us identify any safety events or near-misses that may be related to the EHR or CDS. We will systematically educate them in identification of potential safety events and near-misses and informing us of these events via use of the Feedback Tab in the CDS or email. We will also ask PCPs to notify us of any clinical situations where their clinical judgment differs from the CDS. Use of the Feedback Tab automatically generates an email that is sent to the study team. The study team then discusses this feedback and any necessary actions, and connects with the PCP to answer the question, discuss steps taken to address the issue, or gather additional information and further trouble-shoot. In addition, at HealthPartners, the emails of Drs. [name] and [name] are listed on the CDS interface for providers, and PCPs are encouraged to contact us directly with any questions or concerns if they'd rather not use the Feedback Tab in

the OUD-CDS. At Sites 2 and 3, study teams will determine what email address should be listed on the CDS interfaces for PCPs to contact with questions or concerns. All PCP feedback will be provided to the DSMB twice per year.

This is a minimal risk study. Adverse events and Serious Adverse events are not collected in the context of this trial. ED Visits, hospitalizations, Overdose events and deaths (all cause) will be captured through data pulls.

The site will follow local standard operating procedures (SOPs) for managing any medical or psychiatric emergencies.

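### Secondary outcome 9 includes fatal opioid overdoses but has no death-record source, so overdose deaths with neither an EHR overdose entry nor a claim would be missed

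*Combined protocol and SAP*

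**What the plan says.** - **Outcome.** Sections 2.2, 7.1 and 13.1.2 list, as secondary outcome 9, "Fatal and non-fatal opioid overdoses during the observation period for patients at high risk of OUD". Section 5.2 names fatal and non-fatal overdose among the secondary objectives. Section 2.1 says only that it may be assessed.
- **Source.** Table 1 in 11.1 gives "EHR & Claims data" for opioid overdoses. For all-cause mortality (outcome 8) it gives "EHR data, Claims data, State mortality data".
- **Other source statements.** Section 11.4 names EHR data collected through the decision-support tool, Clarity pulls, surveys and interviews. Sections 15.1 to 15.3 describe no mortality linkage. Section 14.16.2 says "ED Visits, hospitalizations, Overdose events and deaths (all cause) will be captured through data pulls".
- **Unrecorded events.** Section 13.7 says that undocumented care "should not be interpreted as a missing value but rather as indicative of a care process or test not having been performed", and that "absence of utilization indicated by billing claims almost always indicates that the utilization (such as a hospitalization) did not occur". Truly missing observations are taken to be very rare and missing at random.
- **Safety.** Section 13.9 says "We will assess the rates of ED use, hospitalization and opioid overdoses that occur in intervention and control clinics". The DSMB tables in 2.5 list overdose, hospitalization and ED rates and PCP feedback. Neither section lists deaths.

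**The concern.** The plan turns to state records to find deaths, but not for the outcome that includes overdose deaths. Someone who dies of an overdose without reaching care may generate no coded overdose in the EHR and no claim. Such a patient can be a death in outcome 8 and have no overdose in outcome 9.

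Claims only partly close the gap. Claims access was optional for the two added systems (9.2, item 24), and about 40% of Site 1 patients are also members of the system's health plan (9.3).

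Two things are at stake. The fatal part of outcome 9 may be under-counted by an unknown amount. Overdose is also a safety measure, and the listed tables would show overdose rates without the deaths needed to read them.

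**Working it through.** **1. Sources side by side.**

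| Outcome | EHR | Claims | State mortality data |
|---|---|---|---|
| 8, all-cause mortality | yes | yes | yes |
| 9, opioid overdose, fatal and non-fatal | yes | yes | not listed |

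None of 11.4, 13.3.3, 14.16.2 or 15.1 to 15.3 links a death record or a cause of death to outcome 9. The loss is confined to overdose deaths with neither an EHR overdose entry nor a claim. An EHR can carry overdose as the cause of death without an encounter, so a death outside care is not automatically lost.

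**2. No figure to reproduce.** The documents give no overdose rate, fatal share, expected count or power for this outcome. All inputs below are assumptions.

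**3. Does under-capture favour one arm?** Assume 40 overdoses in each arm, 10 of them fatal in usual care, and a share u = 0.3 to 0.8 of fatal overdoses unrecorded. In the intervention arm assume naloxone turns 5 of the 10 deaths into survived overdoses, of which a share r is recorded. All other non-fatal overdoses are taken as recorded.

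- Usual care records 30 + 10(1 − u).
- Intervention records 30 + 5r + 5(1 − u).

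| u | Usual care | Intervention, r = 1 | Ratio | Intervention, r = 0 | Ratio |
|---|---|---|---|---|---|
| 0.3 | 37 | 38.5 | 1.04 | 33.5 | 0.91 |
| 0.8 | 32 | 36 | 1.13 | 31 | 0.97 |

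The ratio exceeds 1 only if 5r > 5u′, where u′ = 1 − u, that is, if r > 1 − u. The sign depends on whether rescued patients reach care and are coded, which the documents do not address. Even the largest ratio is within noise: for 36 against 32 events, SE(log ratio) = √(1/36 + 1/32) = 0.243, giving a 95% interval of about 0.70 to 1.81 before clustering.

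**4. Milder inputs.** Let the fatal share of overdoses be s = 5% to 20%, the unrecorded share of fatal overdoses u = 25% to 75%, and the share of unseen deaths converted to recorded non-fatal overdoses c = 10% to 30%, with equal true totals.

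- Recorded overall ratio = [1 − su(1 − c)] / (1 − su): 1.001 to 1.053.
- True fatal ratio = 1 − uc: 0.975 down to 0.775. The recorded fatal ratio stays at 1.00, because only unseen deaths are converted in this example.

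**5. Precision if the loss is equal in both arms.** The rate ratio is then unbiased. Its standard error grows by 1/√(share of events kept).

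- Fatal overdoses alone: 1.15, 1.41 and 2.00 times for u = 25%, 50% and 75%.
- Fatal and non-fatal combined: su = 1.3% to 15% of events lost, so 1.006 to 1.085 times.

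**The case against.** The strongest reply is that the omission is narrow and its consequences are easily overstated. Several stronger readings are tempting, and the documents do not support them.

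- **That 13.7 expressly codes these deaths as overdose-free.** It speaks of care processes, vital signs, medications and utilization, and names neither overdoses nor deaths. That an unrecorded fatal overdose adds nothing to the count is an inference, although the plan offers no other treatment.
- **That the intervention would be made to look harmful.** This needs rescued patients to be recorded more often than the deaths they replace. With r = 0 the ratio is 0.91 to 0.97.
- **That fatal and non-fatal events are analysed only as one pooled count.** The wording is ambiguous. Section 13.3.3 speaks of rates in the plural, and 13.3 defers detail to a fuller Statistical Analysis Plan.
- **That the DSMB would not see deaths.** They are captured under 14.16.2, and 14.16.1 has the board review accumulating safety and efficacy data. What can be said is that the tables listed in 2.5 do not include them.
- **That outcome 9 cannot serve its objective.** Non-fatal overdoses, and fatal ones with a record, can still be counted, and all deaths are sought under outcome 8.

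These replies stand and limit the point. They do not explain why one row of Table 1 has a death-record source and the row that includes overdose deaths has none.

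**Conclusion.** The point holds as a gap in ascertainment. Followed as written, Table 1 misses overdose deaths with neither an EHR overdose entry nor a claim, and the listed safety outputs omit deaths that the study already captures. Both statements rest on the text and need no numerical assumption.

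The amount lost cannot be computed from the documents. For combined overdoses it may be small. For fatal overdoses alone it could be large. Differential capture by arm is possible, but a reader should not infer a direction: the range of 0.91 to 1.13 straddles 1 and rests wholly on assumed inputs. The outcome is secondary and, under 2.1, optional. Primary analyses are unaffected. The change is worth making because a mortality source is already planned.

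**What to change.** 1. **Table 1 (11.1), opioid-overdose row:** add state mortality data with cause of death, after confirming that the field is available at each site. Define fatal opioid overdose by stated cause-of-death codes.
2. **7.1, 13.1.2 and 13.3.3:** report fatal and non-fatal overdoses separately, as well as combined.
3. **13.9 and the DSMB tables in 2.5:** add all-cause deaths, and fatal overdoses where available.
4. **If cause of death cannot be obtained:** state that fatal overdose is captured only when recorded in the EHR or claims, and interpret outcome 9 alongside all-cause mortality.

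**Cost.** Items 2 and 3 are mainly changes of wording and of tables, since 14.16.2 already provides for capturing deaths. Item 1 may need an added field in the mortality request. The documents do not say that the state files carry cause of death, and Site 1 alone has facilities in two states (9.3). Cause-of-death coding may also lag the fact of death, so late deaths may be classified after the all-cause count is complete.

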5.3 Exploratory Objective(s)

In exploratory analyses, we may assess whether (a) PCPs in intervention clinics who are non-waivered at go-live dates are more likely to become buprenorphine-waivered than PCPs in UC clinics during the intervention period; (b) waived PCPs in intervention clinics are more likely to prescribe buprenorphine than PCPs in UC clinics during the intervention period; (c) whether PCPs in intervention clinics who are non-waivered at go-live dates are reportedly more likely to prescribe buprenorphine should a waiver no longer be required than PCPs in UC clinics measured prior to go-live dates and at 9 months following go-live dates; (d) if we have adequate data, potentially via health plan or Surescripts data, whether adherence/persistence to methadone, buprenorphine, XR-NTX or therapy for patients with OUD differs for patients in intervention vs. UC clinics during the observation period; and (e) PCPs in intervention clinics are more likely to screen their patients for mental health conditions and infectious diseases than PCPs in UC clinics during the intervention period.

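### Exploratory outcomes 5 and 2 are restricted to diagnosed patients and waivered PCPs without dating either status, so arms can differ with no change in screening or per-PCP prescribing

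*Combined protocol and SAP*

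**What the plan says.** Section 7.1 lists exploratory outcomes that may be assessed; sections 2.2 and 13.1.2 repeat them. Three matter here.

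- **Outcome 5** is the "Number of patients diagnosed with OUD screened for mental health comorbidities and infectious diseases during the observation period". It has no denominator, and the diagnosis has no date. The matching objective (e) in section 5.3 is wider: "PCPs in intervention clinics are more likely to screen their patients for mental health conditions and infectious diseases than PCPs in UC clinics".
- **Outcome 2** is the "Number of buprenorphine prescriptions written by waived PCPs during the intervention period". Objective (b) asks whether "waived PCPs in intervention clinics are more likely to prescribe buprenorphine than PCPs in UC clinics during the intervention period". Waiver status has no date, and read literally the sentence sets waivered PCPs in one arm against PCPs in general in the other.
- **Outcome 4** is "Adherence to therapy during the observation period, assessed via Clarity and claims data", with no population named. Objective (d) supplies one when it asks "whether adherence/persistence to methadone, buprenorphine, XR-NTX or therapy for patients with OUD differs", but does not say when the OUD must have been recorded.

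The same list shows that status can be anchored. Objective (a) asks whether "PCPs in intervention clinics who are non-waivered at go-live dates are more likely to become buprenorphine-waivered than PCPs in UC clinics", and objective (c) uses the same go-live anchor.

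**The concern.** The intervention is expected to change the statuses that define these groups. H1.1 predicts more OUD diagnoses, objective (a) predicts more waivered PCPs, and H2.1 predicts more MOUD orders or referrals. If status gained after the index visit or go-live counts, the groups compared are partly products of the intervention, and randomisation no longer makes them alike.

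For outcome 5 there is a specific risk of misreading. Section 4.1 describes a final module of the tool that prompts comorbidity screening, so a higher count would look like that module working when only diagnosis had changed. For objective (b), more prescriptions from waivered PCPs could reflect more such PCPs and not more prescribing by each.

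**Working it through.** **1. The plan's own figure for diagnosis.** Section 13.2.2.1 gives 30 clinics, 50 patients each, ICC 0.03, 5% diagnosed in UC, power 0.80 and two-sided alpha 0.05. The stated minimum detectable rate in OUD-CDS clinics is 11.35% (odds ratio 2.43).

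- Design effect: 1 + (50 − 1) × 0.03 = 2.47.
- Patients per arm at 1:1: 15 × 50 = 750. Effective number: 750 / 2.47 = 303.6.
- Solving p2 − p1 = (sum of the 0.975 and 0.80 quantiles) × √[(p1(1 − p1) + p2(1 − p2)) / 303.6] gives p2 = 11.42% with t quantiles on 28 df and 11.16% with normal quantiles.
- Power at 11.35% is 79.2% (t) or 81.6% (normal). Odds ratio: (0.1135/0.8865) / (0.05/0.95) = 2.43.

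The figure reproduces closely. It is a detectable difference at 30 days, used below only to set a scale.

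**2. Outcome 5 as a count, equal screening in both arms.** Newly diagnosed per 750 high-risk patients: 750 × 0.05 = 37.5 versus 750 × 0.1135 = 85.1. If 40% are screened in each arm (assumed), the counts are 15.0 and 34.1. The screening probability cancels, so the ratio is 0.1135 / 0.05 = 2.27 at any common value.

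Previously diagnosed patients are also eligible (section 8.3) and would be counted. If they are a share w of the sample, the ratio is [w + (1 − w) × 0.1135] / [w + (1 − w) × 0.05].

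| w (assumed) | Count ratio |
|---|---|
| 5% | 0.1578 / 0.0975 = 1.62 |
| 10% | 0.2022 / 0.1450 = 1.39 |
| 20% | 0.2908 / 0.2400 = 1.21 |
| 50% | 0.5568 / 0.5250 = 1.06 |

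**3. Outcome 5 as a proportion of diagnosed patients.** If old and new cases are screened alike, the arm difference is zero. If old cases are screened at 60% and new ones at 30% (assumed), the intervention arm appears 5.9 points lower at w = 5% and 1.6 points lower at w = 50%. Reversing the two rates reverses the sign. Dividing by the number diagnosed therefore does not cure the problem; it makes its direction depend on case mix.

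**4. Outcome 2 and objective (b).** The documents give no prescribing rates, so every input here is assumed: 10 waivered PCPs per arm at go-live, then 2 new waivers in UC and 6 in OUD-CDS.

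- Every PCP writes 20 prescriptions: 12 × 20 = 240 versus 16 × 20 = 320, a ratio of 1.33, with 20 per PCP in both arms.
- New waiver holders write 5: (200 + 10) / 12 = 17.5 versus (200 + 30) / 16 = 14.4 per waivered PCP, although the total is higher in the intervention arm (230 versus 210).
- Restricted to PCPs waivered at go-live: 20 versus 20 per PCP in either case.

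**5. Outcome 4 and objective (d).** Assume 50 continuing patients per arm at 80% adherence, and new starters at 50%. With 10 starters in UC, mean adherence is (40 + 5) / 60 = 75.0%. With 15, 20 or 30 starters in OUD-CDS it is 47.5/65 = 73.1%, 50/70 = 71.4% or 55/80 = 68.8%. Nobody's adherence has changed.

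**6. Whether another section settles it.** Table 1 (section 11.1) gives only timing and data source. Section 13.3.3 gives only the model class for adherence. Section 13.3 leaves detail to the Statistical Analysis Plan, chiefly for primary outcome analyses. None dates the diagnosis or the waiver. A wider denominator is already available: section 6.2 has the algorithms identify eligible patients in both arms whatever the PCP does, and Table 2 (section 11.2) expresses screening as a percentage of eligible patients, though as a monitoring measure.

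**The case against.** The strongest reply is that the documents leave status undated and nowhere say that status gained after index or go-live will define the groups. That is correct: the fault is an opening in the definition, not a stated rule.

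A reader might infer that the adherence comparison in objective (d) includes patients diagnosed because of the alert. The text does not establish this. H2.2 separates patients with OUD from those at high risk according to status at the index visit, so OUD at index is at least as natural a reading. What remains is that adherence can be measured only in patients on therapy. Primary outcome 4, MOUD days covered in all eligible patients, avoids that restriction.

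A reader might also take 2.27 as the expected distortion. It is a worst case: it leaves out previously diagnosed patients and carries a 30-day detectable difference over the whole observation period. Section 13.4 allows that the tool may only speed up actions UC would take later, which would shrink the ratio.

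For outcome 2, a higher total would be a real increase in prescribing by waivered PCPs as a group. It could not show that waivered PCPs prescribe more, which is what (b) asks. Section 10.7 allows waiver incentives in both arms, which may narrow the gap in new waivers. Finally, these outcomes are exploratory and optional.

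**Conclusion.** The concern stands for outcome 5 and for outcome 2 with objective (b). As written, each can show an arm difference with no change in screening or per-PCP prescribing, and no other section prevents it. For outcome 5 the spurious count ratio runs from 1.06 to 1.62 for assumed shares of previously diagnosed patients between 50% and 5%, with 2.27 as the limit when there are none. This rests on the plan's detectable H1.1 difference and equal screening. As a proportion of diagnosed patients the bias can take either sign or vanish. The size for (b) cannot be derived from the documents.

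For outcome 4 and objective (d) the point is weaker: the population is undated, and conditioning on therapy is the firmer ground.

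It would go too far to say that the plan prescribes subsets formed after randomisation, or that its main conclusions are at risk. No primary or secondary test is affected. This is a cheap improvement.

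**What to change.** Change the wording in sections 2.1, 2.2, 5.3, 7.1, 11.1 (Table 1) and 13.1.2:

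- **Outcome 5:** the proportion screened among all algorithm-identified eligible patients, which agrees with objective (e) and Table 2. Add a supporting analysis in patients whose OUD was documented before the index visit.
- **Outcome 2 and objective (b):** PCPs waivered at go-live in both arms, plus buprenorphine prescriptions per clinic from all PCPs.
- **Outcome 4 and objective (d):** patients with OUD or on MOUD before the index visit.
- **Any subset formed after index or go-live:** label it descriptive.
- **Outcome 4 timing and source:** reconcile section 7.1 (observation period; Clarity and claims) with Table 1 (intervention period; EHR/OUD-CDS data).

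No new data collection is needed. Prior OUD and current MOUD are eligibility criteria (section 8.3), and Table 1 includes pre-intervention waiver status. The cost is precision: the baseline-OUD and baseline-waiver subsets are smaller.
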